8.3.2. Secondary endpoints

All efficacy endpoints will be described in both study cohorts (AR-V7-negative and positive) and combining both cohorts.

All efficacy endpoints will be evaluated at the first 34 months period of the study. Additionally, OS will be evaluated at the 2-years safety extension after the end of the treatment. The other efficacy endpoints will not be evaluated at the 2-years safety extension.

-OS defined as the time from inclusion until death from any cause or the last date the patient was known to be alive.

Patients who are lost to follow-up and the patients who are alive at the date of data cut-off are censored at the date the patient was last known alive. Censoring rules are specified in **Table 3**.

- Time to first SSE defined as the time from treatment initiation until SSE (pathological fractures, vertebral or non-vertebral, spinal cord compression, radiation or surgery to bone). For all other events, the start date of the event/medication/therapy was used as the time of the event. If an event has not occurred at the time of the analysis or the patient has been lost to follow-up, the time-to-event variables will be censored at the last disease assessment date.

- Alkaline phosphatase level response, normalization of alkaline phosphatase level(progression defined as FAelevation \geq 25% after 12 weeks).

- The time from the first study drug administration to when PSA progression was observed, defined as: 1) In subjects with no PSA decline from baseline; a greater than or equal to 25% increase from baseline value and an increase in absolute value of greater than or equal to 2 ng/mL, at least 12 weeks from baseline; 2) In subjects with initial PSA decline from baseline; the time from start of treatment to first PSA increase that is greater than or equal to 25% increase and at least 2 ng/mL above the nadir value, which was confirmed by a second value obtained three or more weeks later.

- Determination percentage of PSA progression(defined as PSA elevation \geq 25% and \geq 2 ng/mL after 12 weeks).

-Radiographic progression-free survival (rPFS) depending on AR-V7 status

Predictive biomarkers

- Assessment of AR-V7 mutation prior to the start of study treatment and at time to documented progression disease or treatment end (see Appendix 3).

-Determination changes in CTCs number prior to the start of study treatment and at time to documented progression disease or treatment end (see Appendix 3).

Table 3. Censoring rules for OS

Situation	End date	Status
Death during study follow-up	Date of death	Death
The patient is alive at last follow-up	Date of last follow-up	Censored

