2.2. Secondary objectives

- Safety profile.
- To determine the association between AR-V7 status (positive vs. negative) and PFS.
- To establish the relationship between CTCs number with radium-223 efficacy.

Secondary endpoints:

Safety

AEs will be evaluated using the Common Terminology Criteria for Adverse Events(CTCAE) of the US National Cancer Institute (NCI) version 4.0[20]. Grade 3 or 4 AEs and serious adverse events (SAEs) will be assessed to determine the safety and tolerability of the various combinations of drugs.

Efficacy

- Radiographic progression-free survival (rPFS) depending on AR-V7 status.
- Overall survival (OS).
- Time to first symptomatic skeletal event (SSE).
- Time to PSA progression according to the ALSYMPCA study criteria.
- Determination percentage of PSA progresion.
- Alkaline phosphatase level response (AF), normalization of alkaline phosphatase level, according to the ALSYMPCA study criteria.

Molecular aspects

- Assessment of AR-V7 mutation evolution during the study treatment.
- Determination changes in CTCs number during the study treatment.

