3.7. EoS

The EoS is defined as the Last Patient LastVisit (LPLV) at the end of the safety follow-up period (24 months after last dose of treatment). This is the last timepoint for data collection.

The last visit for efficacy evaluation will be take place within three following months after last patient's disease progression, death, withdrawal of consent or 34 months after the first patient has been included, whichever occurs first.

The last visit for safety and overall survival evaluation will be take place 2 years after last dose of study treatment of last patient. We include a 2-years extension after the end of the treatment to evaluate symptomatic skeletal related events. Additionally, analysis of overall survival will be also extended. Contact by telephone is permitted.

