7.2. Reporting of AEs

AEs will be collected starting from the first procedure required by the study up to three months after patient's disease progression. Safety evaluation after progression will include follow-up of symptomatic skeletal related events until reach 2 years from the last dose of study treatment.

All study patients who experience AEs will be closely monitored during this time. All AEs should be recorded in the CRF.

All signs, symptoms, and results of procedures with abnormal diagnoses that are clearly related should be grouped together and reported as a single diagnosis or disorder wherever possible. Any other event that does not fulfill this definition will also be reported separately.

Reporting of SAEs and reporting period

Reporting requirements will comply with all applicable local regulations regarding safety reporting.

All SAEs and AESIs defined in the protocol will be reported to the Sponsor within a period of 24 hours from the time the investigator or any other member of the site staff becomes aware of the event, as follows:

- Regardless of the study drug received by the patient and whether or not the investigator considers this event to be related or not to the study drug, all SAEs and AESIs (as defined in this protocol), will be reported to MedSIR immediately, no later than 24 hours after any member of the study site staff becomes aware of the event.
- All information regarding the SAE and AESI should be obtained and recorded in full using the SAE form and sent to MedSIR.
- Follow-up information, copies of test results, event outcome and the opinion of the investigator as to the relationship between the IMP and the SAE and AESI, accompanied by other applicable documentation when it is requested, will be sent along with the SAE form, if available on the day the event is reported or as soon as possible if it is not.
- The original SAE reporting form of the Sponsor should be kept on file with the documentation from the CRF at the study site(s).

All SAE forms will be sent by the investigator or investigator staff to the Sponsor by e-mail and fax as indicated below:

E-mail: [contact]

Fax: [name]

Follow-up of the SAEs and AESIs will continue until they resolve, a stable outcome is reached, patient is lost to follow-up, or the patient dies.

MedSIR will be responsible for ensuring that events are reported to the European Medicine Agency (EMA), competent authorities, within the stipulated period, as needed.

AESIs

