8.5. Safety results

All safety data will be evaluated at the first 34 months period of the study. Additionally, symptomatic skeletal related events will be evaluated at the 2-years safety extension after the end of the treatment.

Analysis of safety-related data will be considered at three levels:

- First, the degree of exposure (dose, duration, number of patients) will be assessed to determine the degree to which study safety can be assessed.
- Second, clinically relevant tests, concomitant medications, and reported AEs will be described. For AEs, severity, expectedness, causality, relationship, body system, action taken, and outcome will be reported.
- Third, SAEs, deaths, and study discontinuations for each study group will be described and assessed.

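### Time to first symptomatic skeletal event is frozen at month 34, although the two-year extension is run to follow those events; opening the extension to it also needs a new censoring date

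*Protocol*

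**What the plan says.** Protocol 8.3.2 sets the general rule, "All efficacy endpoints will be evaluated at the first 34 months period of the study", then one exception, "Additionally, OS will be evaluated at the 2-years safety extension after the end of the treatment", then the bar, "The other efficacy endpoints will not be evaluated at the 2-years safety extension". SAP 7.2 repeats all three. Both documents list time to first SSE under Efficacy among the secondary endpoints (protocol 2.2, SAP 5.2). Its planned analysis is a Kaplan-Meier description with a log-rank comparison by AR-V7 status (protocol 8.4; SAP 7.2.1 and 7.2.2).

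Protocol 3.7 gives the reason for the extension: "We include a 2-years extension after the end of the treatment to evaluate symptomatic skeletal related events". Protocol 7.2 sets the collection period: "Safety evaluation after progression will include follow-up of symptomatic skeletal related events until reach 2 years from the last dose of study treatment". Protocol 5.3 and Appendix 1 note 13 schedule two contacts after progression, one within three months of it and one 24 months after the last dose.

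Protocol 8.5, on safety, says that "symptomatic skeletal related events will be evaluated at the 2-years safety extension after the end of the treatment". It names no method. SAP 7.3, the matching section, speaks of bone lesions instead, as do protocol 8.2 and SAP 4.7 when they describe the extension.

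For patients without an SSE, protocol 8.3.2 and SAP 7.2.1 censor at the last disease assessment. Scheduled radiological assessments end at progression (protocol 5.3, Appendix 1 note 12).

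**The concern.** Overall survival, which protocol 3.7 adds as a further use of the extension, gets the longer analysis. The event named as the reason for the extension does not. No sentence in either document lets the Kaplan-Meier estimate of time to first SSE use an event that occurs after month 34.

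A safety tabulation does not replace that estimate. Patients enter over 23 months, so follow-up at month 34 ranges from 11 to 34 months, and a count or percentage ignores the difference. What is at stake is the precision and reach of the only planned analysis that estimates how SSE risk develops over time.

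**Working it through.** **The plan's own figures.** The documents give no sample size, event count, median or precision for time to first SSE, so there is no SSE figure to reproduce. The timing figures in protocol 8.2 agree with each other: 23 + 11 = 34 months, and 2.26 x 23 = 51.98, or 52 patients.

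**Follow-up cut off at month 34.** A patient entering at month u (uniform on 0-23) has 34 - u months of follow-up. Six injections four weeks apart span 20 weeks, or 4.6 months. Planned SSE follow-up is therefore 4.6 + 24 = 28.6 months if all doses are given.
- It is incomplete when u > 34 - 28.6 = 5.4. The share is (23 - 5.4)/23 = 0.765, about 40 of 52 patients.
- The largest amount left out is 28.6 - 11 = 17.6 months. The mean is 17.6^2/(2 x 23) = 6.7 months.

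These figures ignore death and early stopping of treatment. If the last dose is taken as the earlier of 20 weeks and progression, about 35-37 of 52 patients have their 24-month contact after month 34. Only about 15-22 of these are alive at month 34, for an assumed OS median of 15-25 months.

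**Expected first SSEs, continuous ascertainment.** With exponential SSE hazard s and death hazard d, the chance of a first SSE by time x is

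F(x) = s/(s + d) x [1 - exp(-(s + d)x)].

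Example: for an SSE median of 12 and an OS median of 24, s = 0.0578 and d = 0.0289. Then 52 x F(28.6) = 52 x 0.667 x (1 - exp(-2.48)) = 31.8. Averaging 52 x F(min(34 - u, 28.6)) over entry gives 28.7 at month 34. The gain is about 3 events, or 10%. With an OS median of 15 and an SSE median of 12, the count goes from 25.3 to 27.4, about 2 events or 8%.

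**Both readings of ascertainment.** Twelve scenarios were simulated: PFS median 3 or 6.3, OS median 15 or 25, and first-SSE median 12, 20 or 30 months, with the last dose as above. The PFS medians are the null and target values in protocol 8.2; the OS and SSE medians are assumptions. On the log-hazard scale, interval width goes as 1/sqrt(events), so the month-34 interval is wider by the square root of the event ratio.

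| SSE status known at month 34 | Gain in first SSEs | Month-34 interval wider by |
|---|---|---|
| Continuously | 7-16% (about 2-3 events) | 3-8% (sqrt 1.07 = 1.03; sqrt 1.16 = 1.08) |
| Only through scheduled contacts | 33-69% (9-23 rising to 15-32 events) | 15-30% (sqrt 1.33 = 1.15; sqrt 1.69 = 1.30) |

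One scheduled-contacts scenario (PFS 6.3, OS 15, SSE 20): 14.2 rises to 19.8, ratio 1.39, square root 1.18.

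**AR-V7.** Protocol 8.2 expects 13 of 52 positive (25%). At equal SSE rates, a gain of 2-3 events puts 0.5-0.75 of an event in the positive group. The 5.6 extra events of the scenario just shown put 5.6 x 0.25 = 1.4 there.

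**Censoring date.** Read the last disease assessment as falling at progression. If the analysis is simply repeated after the extension, late SSEs count as events while event-free patients leave the risk set at progression. In the same simulations, a true SSE median of 20 months is then estimated at 10.8-13.4 months, and a true 12 at 8.4-9.8. The month-34 analysis has the same fault (10.7-13.9 and 7.7-9.4), so a later data cut alone does not repair it.

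**The case against.** The strongest reply is that the extension is labelled a safety extension throughout, and that late SSEs may follow other anticancer therapy begun after progression. Fixing the efficacy estimate at month 34 and reporting later SSEs as safety data would then be a defensible choice. The point about later therapy stands and belongs in the report. But neither document gives this reason, and overall survival, which later therapy also affects, is extended.

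A reader might infer that the extension SSEs go unanalysed. Protocol 8.5 says otherwise. What is missing is a time-to-event analysis of them.

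A reader might also take one-third to two-thirds more events as the size of the loss. That needs SSE status to be unknown between the post-progression visit and the 24-month contact. Appendix 1 note 13 lists only those contacts. Yet protocol 7.2 has SSE follow-up run to two years after the last dose, protocol 3.3 records medication for SSEs until end of study, and protocol 8.7 has patient data reviewed at least every four months. The documents do not settle which reading applies, so the full range should be given.

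Nor do the documents support a material loss for the AR-V7 comparison. The positive group is small, and SAP 7.2.1 and 7.2.2 already fall back on description if very few such patients are recruited.

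**Conclusion.** The point holds. Both documents exclude time to first SSE from the extension, while protocol 3.7 and 7.2 run the extension to follow those events. The loss is modest, about 2-3 first SSEs, if sites report SSEs continuously, and substantial, up to about 69% more events, if they are learned of only at the scheduled contacts. About 15-22 patients would be alive at month 34 with the 24-month contact pending. All event counts rest on assumed exponential medians, with SSE, progression and death taken as independent.

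It would be wrong to conclude that moving the analysis date is enough. Under the present censoring rule, the later estimate would still be biased toward early SSEs. That bias rests on reading a disease assessment as a tumour assessment, a term that the documents leave undefined. This is a secondary-endpoint matter: the primary analysis, the sample size and the rule for declaring the study positive do not depend on it.

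**What to change.** In protocol 8.3.2 and SAP 7.2, name time to first SSE beside overall survival as an endpoint to be re-estimated at the end of the two-year extension. Repeat the Kaplan-Meier estimate and the AR-V7 comparison then, and keep the month-34 result as the first report.

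In the SSE definition in protocol 8.3.2 and SAP 7.2.1, replace the last disease assessment as the censoring date with the last date on which SSE status was known, or the date of death for a patient who died without an SSE. Apply this at month 34 as well, since the same bias arises there.

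The cost is two short text changes in each document and one extra run of a planned analysis. No new visits are needed, because the contacts are already scheduled, but the date of last known SSE status must be available in the data. The report should note that later SSEs may occur after other anticancer therapy.

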8.3.3. Analysis sets

We propose to test efficacy and safety of experimental treatment using the full analysis set. We include in the analysis all patients that accomplished selection criteria and receive one drug exposure.

8.3.4. Analysis of baseline and demographic variables

The demographics and baseline characteristics including disease history and prior therapy are summarized using descriptive statistics.

8.3.5. Efficacy analysis

Tumor response, bone lesion, SSE evaluation, biochemistry determinations, and predictive biomarkers are obtained at investigators' sites. There is not central and independent review of evaluations. Methodology for tumor assessment will be according to the RECIST version 1.1 and the PCWG2 criteria.

8.3.6. Decision rules and adjustment of alpha for primary endpoint

The study will be declared positive if the median PFS of radium-223 in total sample is statistically significantly better compared with null hypothesis ($p < 0.05$).

8.4. Efficacy results

Primary endpoint

We will analyze PFS in both cohorts with one arm Log-Rank test. This time endpoint will be described with Kaplan-Meier method. We will calculate number and proportion of events and median survival time, with corresponding 95% CI.

Secondary endpoints

We will describe the number and percentage of patients with AR-V7 mutation and CTCs at the start and at the end of the study. The evolution of these measures in the study will be analyzed with McNemar's test and paired odds ratio (OR) with corresponding 95% CI.

OS, time to first symptomatic SSE, rPFS and alkaline phosphatase level response (AF) will be described with Kaplan-Meier method. Number and proportion of events and median survival time, with corresponding 95% CI, will be calculated.

Subgroup analysis

The AR-V7-negative and positive cohorts at baseline will be compared for all analysis. For timed endpoints (PFS, OS, time to first symptomatic SSE, TTP-AF, and TTP-PSA), we will use the Kaplan-Meier method and Log-Rank test. For binary outcomes we will use chi-squared or Fisher's exact tests.

Levels of CTCs at the start and at the end of the study will be correlated with timed and binary endpoints. For timed and binary endpoints we will use Cox analysis and logistic regression, respectively.

We also analyse PFS and OS with multivariable Cox proportional hazards models for adjusting for AR-V7 status, CTCs levels and relevant baseline covariates, including Gleason score, PSA level, number of prior hormonal treatments, the presence or absence of visceral metastases, the Eastern Cooperative Oncology Group (ECOG) score, prior use of abiraterone acetate or enzalutamide, and the level of full-length (FL) androgen receptor. All tests were two-sided, and P values of 0.05 or less were considered to indicate statistical significance. We will examine the residuals to assess model assumptions and only first-order interactions will be evaluated. We will calculate relative risk (RR) and HR with corresponding 95% CI to compare dichotomous and time to event variables, respectively. Up-to-date versions of R will be used to conduct analyses.

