- Basic blood test that includes blood count, coagulation, chemistry with renal function analysis (serum creatinine, creatinine clearance according to the Cockcroft-Gault formula), liver function (AST, ALT, AF, GGT, total and direct bilirubin), glucose, sodium, potassium, calcium, chloride, magnesium, uric acid, total protein, albumin, and lactate dehydrogenase.
- PSA determination.
- HRQoL questionnaire(FACT-P, Version 04).
- Assessment of concomitant medications.
- Assessment of AEs.
- Tumor assessment: torax, abdomen, and pelvisCT scan or MRI, and bone scan prior to start of cycle every three cycles, every 12 weeks, until progression disease.
- Survival.

Blood assessment schedule for translational study:

- Blood draws prior to the start of study treatment, at the end of treatment and at the time to documented progression disease.

Biological sampling:

The first blood samples should be taken before starting study treatment (see appendix3 for more details on blood sampling procedures). The following samples should be taken at the end of treatment and at the time of disease progression.

At the time of site activation, the Sponsor will provide streck cell-free DNA BCT tubes as well as labels for the storage and transport of samples. No other tubes or labels should be used for this study. If more tubes and labels are required, these should be requested from the Sponsor in writing at least three weeks before they are required (see appendix 3).

Anamnesis and demographic data:

Anamnesis includes clinically significant diseases, surgical interventions, history of cancer (including prior antineoplastic treatments and procedures), history of smoking, alcoholism, drug addiction, as well as any medications (e.g., prescribed drugs, over-the-counter drugs, medicinal plants, homeopathic remedies, or food supplements) used by the patient in the 28 days prior to screening visit. Demographic data will include age, sex, and self-reported race/ethnicity.

Vital signs:

These will include the measurement of height (only during screening), weight, respiratory rate, heart rate, blood pressure, and body temperature. Abnormal or significant changes in vital signs from baseline should be recorded as AEs, if appropriate.

Physical Examination:

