 - 4. ECOG performance status will be assessed before trial drug administration and before the administration of each cycle.
 - 5. Relevant concomitant medication will be recorded at screening and on an ongoing basis.
 - 6. FACT-P, Version 04
 - 7. All AEs occurring during the trial and until the treatment discontinuation visit (end of study visit) have to be recorded with grading according to NCI-CTCAE version 4.0.
 - 8. Baseline assessments of the thorax, abdomen, and pelvis (preferably CT or MRI in case of contrast allergy) must be performed no more than 28 days before the first trial treatment. Baseline bone scan must be performed no more than 28 days before the first trial treatment. Post-baseline assessments have to be performed every 12 weeks \pm 7 working days after the first dose using the same imaging method and where possible obtained at the same institution for an individual patient as used during screening until progression disease. Radiographic bone progression will require the persistence of new lesions on a confirmatory scan at least six weeks later. In those patients who receive 6 treatment cycles, the radiological tumour assessment corresponding to week 24 will be performed for the EOT visit.
 - 9. Hematological test will be performed as per local standard of care and clinical indication before treatment administration. These values should be included: hemoglobin, hematocrit, red blood cell count, platelet count, and white blood cell count with differential count (neutrophils, lymphocytes, monocytes, eosinophils, and basophils).
 - 10. Biochemistry test will be performed as per local standard of care and clinical indication before first treatment administration and first day of follow-up. These values should be included: coagulation, chemistry with renal function analysis (serum creatinine, creatinine clearance according to the Cockcroft-Gault formula), liver function (AST, ALT, ALP, direct and total bilirubin), glucose, sodium, potassium, calcium, chloride, magnesium, uric acid, total protein, albumin, and lactate dehydrogenase.
 - 11. Blood sample for central laboratory prior to the start of study treatment, at the end of treatment and at time to documented progression disease (if the patient ends treatment due to progressive disease, only one blood sample will be sent at this point).

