#### **7.2.2 Subgroup Analysis**

The AR-V7-negative and positive cohorts at baseline will be compared for all analysis. All subgroup analysis will be based on the full analysis and per protocol sets. If there are very few AR-V7 patients recruited, outcomes will be only described.

For time to event endpoints (PFS, OS, time to first symptomatic SSE, TTP-AF, and TTP-PSA), we will use the Kaplan-Meier method and Log-Rank test. For binary outcomes we will use Chi-squared or Fisher's exact tests.

We also analyze PFS and OS with multivariable Cox proportional hazards models including AR-V7 status, CTCs levels and other relevant baseline covariates, including PSA level, number of prior hormonal treatments, the presence or absence of visceral metastases, the Eastern Cooperative Oncology Group (ECOG) score, and prior use of abiraterone acetate or enzalutamide. All tests were two-sided, and P values of 0.05 or less were considered to indicate statistical significance. We will examine the residuals to assess model assumptions and only first-order interactions will be evaluated. We will calculate relative risk (RR) and HR with corresponding 95% CI to compare dichotomous and time to event variables, respectively.

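### Protocol 8.4 enters end-of-study CTC level in Cox models whose clock starts before the sample is taken; for PFS, the timing of that sample depends on the outcome

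*Protocol*

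**What the plan says.** Protocol 8.4, under Subgroup analysis, states: "Levels of CTCs at the start and at the end of the study will be correlated with timed and binary endpoints". The models follow: "For timed and binary endpoints we will use Cox analysis and logistic regression, respectively". The same section lists the timed endpoints: "For timed endpoints (PFS, OS, time to first symptomatic SSE, TTP-AF, and TTP-PSA". It sets the test level: "All tests were two-sided, and P values of 0.05 or less were considered to indicate statistical significance".

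Protocol 5.2 gives the sampling times: "Blood draws prior to the start of study treatment, at the end of treatment and at the time to documented progression disease". Appendix 1, note 11, agrees ("at the end of treatment and at time to documented progression disease") and adds that a patient whose treatment ends because of progression sends only one sample at that point. Protocol 8.3.2 describes the marker endpoint as "Determination changes in CTCs number prior to the start of study treatment and at time to documented progression disease or treatment end". Section 5.3 allows up to 28 days after progression or end of treatment for these assessments, blood sample included. Appendix 1, note 8, ties the end-of-treatment visit to week 24 for patients who receive six cycles.

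PFS is timed from the start of radium-223 (8.3.1) and OS from inclusion (8.3.2).

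SAP 7.2.2 has no start/end CTC sentence and no logistic model for CTC. Its multivariable Cox model for PFS and OS includes "CTCs levels and other relevant baseline covariates". SAP 5.2 keeps the secondary objective relating CTC number to efficacy, and SAP section 6 keeps an analysis set for CTC.

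**The concern.** A fixed covariate in a Cox model must be known when the clock starts. The later CTC value is not. For a patient who progresses on treatment it is obtained because the PFS event has occurred, at the event or shortly afterwards. For a patient who completes treatment it is obtained at about week 24, with the event still to come. If CTC tends to be higher at progression, or simply drifts with time on treatment, early progressors will differ in CTC from the others even when CTC has no bearing on the hazard.

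For OS the sample precedes death, so the fault is different: a value measured after time zero is treated as if it had been known at time zero.

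What is at stake is a named secondary objective, the relation of CTC number to radium-223 efficacy. Neither document provides a landmark, a time-dependent covariate or a reset time origin. Nor do they say which sample counts as the end value when a patient has both an end-of-treatment and a progression sample.

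**Working it through.** **The plan's own figure.** The documents give no sample size or power for the CTC analysis. The figure to reproduce is N = 52, which is also the simulation size. Inputs from Protocol 8.2: medians 3 and 6.3 months, one-sided alpha 0.05, 80% power, accrual A = 23 months, follow-up F = 11 months, 25% AR-V7-positive.

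- Events = (z0.95 + z0.80)² / [ln(3/6.3)]² = 11.23.
- With λ = ln 2/6.3 = 0.110, P(event) = 1 − [exp(−λF) − exp(−λ(A+F))]/(λA) = 1 − (0.298 − 0.024)/2.53 = 0.892.
- 11.23/0.892 = 12.6, rounded up to 13; 13/0.25 = 52. This matches.

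**Position of the later sample** (Protocol 5.2, 5.3, Appendix 1)

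| Patient | Later sample | Relative to PFS event | Relative to death |
|---|---|---|---|
| Progresses on treatment | One sample serving both purposes | At, or up to 28 days after | Before |
| Completes or stops without progression | End-of-treatment sample | Before | Before |
| Same patient, if progression follows | Second sample at progression | At, or up to 28 days after | Before |

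**How many patients.** Assume exponential PFS with median m. Week 24 is 24/4.345 = 5.52 months, and the share progressed is 1 − 2^(−5.52/m).

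- m = 6.3: 46% progressed; event-free 0.545 × 52 ≈ 28.
- m = 3: 72% progressed; event-free 0.279 × 52 ≈ 15.

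**Simulation under no CTC effect.** 1,500 trials per scenario, n = 52, univariable Cox, two-sided 0.05, end sample at the first of progression or week 24. Assumptions that are not in the documents: baseline-to-end CTC correlation 0.7, the CTC changes in the first column, and a median of 12 months from progression to death. Cells give rejection rates at median PFS 3 / 6.3 months. The Monte Carlo standard error at 5% is √(0.05 × 0.95/1500) = 0.6 points.

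| Assumed CTC change | End CTC, PFS | End CTC, OS | Baseline CTC, PFS | Week-24 landmark, PFS |
|---|---|---|---|---|
| None | 4.3 / 5.4% | 5.1 / 6.1% | 4.8 / 5.9% | 4.4 / 6.3% |
| +0.5 SD at progression | 24.2 / 22.1% | 6.5 / 7.7% | 5.6 / 4.4% | 5.5 / 5.2% |
| +1 SD at progression | 68.8 / 66.4% | 9.1 / 18.3% | 6.1 / 6.5% | 5.3 / 4.9% |
| −0.1 SD per month | 21.5 / 14.9% | 5.5 / 6.2% | 5.7 / 5.4% | 4.9 / 5.5% |
| −0.2 SD per month | 63.7 / 39.7% | 8.9 / 10.7% | 5.6 / 4.4% | 4.6 / 4.7% |

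The mean spurious PFS hazard ratio per baseline SD was 1.21 for the 0.5 SD rise and 1.40–1.43 for 1 SD. A second simulation (1,000 trials, median 6.3 months, end sample by 5.5 months) gave 23% and 62% for the same two rises. Restarting the OS clock at each patient's sample date gave 5.0–12.9% across the scenarios with a CTC change.

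**The case against.** The best defence is the SAP. Its section 7.2.2 follows the protocol's subgroup text closely but leaves out both CTC sentences, and its wording places CTC among the baseline covariates. SAP 8.2 defines baseline as the last valid value before first drug. Later CTC values appear explicitly only in descriptive summaries and in McNemar's test of evolution. An analyst working from the SAP alone would probably use baseline CTC. This stands as mitigation and is not a cure. The protocol analysis is nowhere withdrawn, the objective it serves is kept, and the Cox text never states the CTC timepoint.

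A reader might also infer more than the documents support:

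- *That the value is measured at or after the event for PFS and OS alike.* Every sample precedes death. For PFS the statement holds for patients who progress on treatment; those who stop or finish without progression give an end-of-treatment sample before any PFS event.
- *That logistic regression will be applied to PFS or OS.* Protocol 8.4 reserves it for binary endpoints and lists PFS and OS as timed.
- *That a false association is certain.* It depends on CTC changing over time or at progression. No document gives the size of such a change, and without one there is no inflation.

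**Conclusion.** The point holds for the protocol text. As written, 8.4 can produce a false association between end-of-study CTC and PFS, because the covariate is sampled at a time set partly by the outcome. With no true effect and n = 52, simulated rejection is 22–24% for an assumed 0.5 SD rise at progression, 62–69% for 1 SD, and 15–64% for an assumed fall of 0.1–0.2 SD per month. Baseline CTC stays near 5%. For OS the fault is a covariate measured after time zero, with rejection of 5.5–18%. The binary endpoints were not simulated.

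These sizes rest on exponential PFS, on the assumed CTC shifts, and on taking the first of progression or week 24 as the end sample. Since change in CTC number is itself a planned endpoint, the plan should allow for change. The analysis is secondary: the primary endpoint, its decision rule and N = 52 are untouched. It should be corrected, and the two documents reconciled.

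**What to change.** - Protocol 8.4: limit the fixed-covariate Cox and logistic models to baseline CTC.
- SAP 7.2.2: write 'baseline CTC level' in the Cox model and state that the regression on end-of-study CTC is withdrawn.
- Both documents: report end-of-treatment CTC descriptively, and say which sample is meant when end-of-treatment and progression samples both exist.
- Optional: a landmark analysis at the end-of-treatment sample among patients still event-free, with OS timed from the sample. Restarting the OS clock without restricting to event-free patients left up to 12.9% rejection in the simulation, so keep the restriction.

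The cost is wording only; no new data are needed. The optional landmark analysis loses patients with earlier events and would rest on about 15–28 of 52 at week 24.
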